5.0 Investigational Plan

5.1 Overall Study Design and Plan: Description

This is an open-label, single arm, Phase 3b, multi-center study evaluating the efficacy of venetoclax monotherapy in relapsed/refractory CLL.

This study is designed to enroll approximately 250 subjects to meet scientific objectives without enrolling an undue number of subjects in alignment with ethical considerations. All efforts will be made to adhere to these specific enrollment numbers; however, it would not be ethical to deny treatment to eligible subjects already in screening as they may have undergone study related procedures.

Subjects in this study will be enrolled at approximately 67 research sites globally.

Subjects will undergo screening procedures within 28 days prior to initial venetoclax administration. For all subjects, a contrast computed tomography (CT) scan (or medically indicated alternative such as magnetic resonance imaging [MRI]) will be accepted if previously performed within 35 days prior to venetoclax administration. Otherwise, a CT scan (or MRI) must be performed within the screening period of 28 days. Following the 4-week Screening period, eligible subjects will initiate venetoclax and attend study visits within 72 hours of dosing and on the first and second day of Week 1 and Week 2 during the dose titration phase. Beginning on Week 3, through Week 5, study visits will be conducted within 72 hours of dosing and on Day 1 of each week. Additional study visits on Day 2 of each week should be performed for subjects who continue to be at risk for TLS, based on investigator assessment. Study visits will be reduced to a monthly frequency at Week 8, and at Week 48, they will be reduced to every 3 months until the end of study treatment (Week 108). As of Week 8, the visit window for scheduled visits is ± 2 days. A 30 day Safety Follow-up Visit should be performed approximately 30 days (± 3 days) following the last dose of venetoclax (to allow for AE collection 30 days following last dose of study drug). If a subject is discontinued from the study with an ongoing AE or an unresolved clinically significant laboratory result, the site will attempt to provide follow-up until the AE has resolved to a \leq Grade 1 or baseline or it is the investigator's judgment that the event is unlikely to resolve.

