The results of the labs drawn on Week 1 Day 1 need to be reviewed prior to dosing **IF** an additional lab draw within 72 hours of the initial dose at Week 1 Day 1 was not drawn **AND** reviewed.

Prior to Each Subsequent Dose Increase, for all Subjects:

- Within 72 hours of each subsequent dose increase: The chemistry/hematology panel should be repeated. The results should be reviewed prior to dose increasing.
- Prior to dosing, on the day of each subsequent dose increase: Before dosing, the chemistry/hematology panel should be drawn. The results of the labs drawn on Day 1 of each dose increase need to be reviewed prior to dosing **IF** an additional lab draw within 72 hours of the dose increase was not drawn **AND** reviewed.

POST-DOSE LABS:

For all subjects, the chemistry/hematology panel (refer to [Table 4](#), Clinical Laboratory Tests) should be monitored at 6 to 8 hours and at 24 hours after the first dose of venetoclax (20 mg) and after the first dose increase (50 mg). Electrolyte abnormalities should be corrected promptly. The next venetoclax doses (the Day 2 20 mg venetoclax dose and the Day 2 50 mg venetoclax dose) should not be administered until the 24 hour lab results have been evaluated. Electrolyte abnormalities should be corrected promptly. For subjects who continue to be at risk of TLS, the same lab monitoring schedule (i.e., 6 to 8 hour and 24-hr post dose) should be followed at the subsequent dose increases.

This monitoring is also recommended during the re-initiation of the therapy after a dose interruption.

Additional monitoring may be required based on the risk assessment by the investigator and as directed by the AbbVie TA MD.

Local laboratories will be utilized to process and provide results for clinical laboratory tests allowing for immediate subject medical management. The principal investigator or sub-investigator will review, initial, and date all laboratory results used for subject treatment management after receipt from the local laboratory. Local laboratory values will be entered by the site directly onto the appropriate eCRF and laboratory normal ranges for the laboratory that is used will be provided to the AbbVie Clinical Team.

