5.5 Treatments

5.5.1 Treatments Administered

Venetoclax tablets should be taken orally once daily with a meal and water in the morning at approximately the same time each day. Venetoclax tablets should be swallowed whole and not chewed, crushed, or broken prior to swallowing.

If the subject misses a dose of venetoclax within 8 hours of the time it is taken, the subject should take the missed dose as soon as possible on the same day and resume the normal daily dosing schedule the following day. If a subject misses a dose by more than 8 hours, the subject should not take the missed dose and resume the normal daily dosing schedule the following day.

In cases of vomiting after taking venetoclax, no additional dose (tablets) should be taken that day. The next dose should be taken at the usual time the following day.

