6.1.8 Toxicity Management

6.1.8.1 Prophylaxis and Management of Tumor Lysis Syndrome

Venetoclax can cause rapid reduction in tumor and thus poses a risk for TLS in the initial 5-week dose-titration phase. Changes in electrolytes consistent with TLS that require prompt management can occur as early as 6 – 8 hours following the first dose of venetoclax and at each dose increase.

Risk Assessment for tumor lysis syndrome: The risk of TLS is a continuum based on multiple factors, including tumor burden and comorbidities. Subjects with high tumor burden (e.g., any lymph node with a diameter ≥ 5 cm or high absolute lymphocyte count [ALC $> 25 \times 10^9/L$]) are a greater risk of TLS. Reduced renal function (creatinine clearance [CrCl] < 80 mL/min) further increases the risk. The risk may decrease as tumor burden decreases with venetoclax treatment.

Additional comorbidities may further increase the risk for TLS.

Prior to initiating venetoclax, tumor burden assessment, including radiographic evaluation (refer to Section 5.3.1.1 Study Procedures – CT scans) must be performed for all subjects during Screening. The full blood chemistry/hematology panel (refer to Table 4 Clinical Laboratory Tests) should be performed in all subjects during the Screening period in order to assess eligibility and to correct pre-existing abnormalities.

If the chemistry/hematology panel was assessed more than 72 hours prior to the 1st dose of venetoclax, an additional full lab panel should be performed and reviewed within 72 hours prior to dosing in order to make a treatment decision.

Prophylaxis for tumor lysis syndrome: The prophylaxis measures listed below should be followed. More intensive measures (including hospitalization) should be employed as overall risk increases:

Hydration:

Subjects should be adequately hydrated prior to starting treatment with venetoclax and during the dose-titration phase. The recommended volume is 1.5 to 2.0 L (approximately 6 to 8 glasses) of water each day. Subjects should be instructed to drink water starting 2 days before and on the day of the first dose, and every time the dose is increased. Intravenous (IV) fluids should be administered as indicated based on overall risk of TLS or for those who cannot maintain an adequate level of oral hydration. For subjects for whom volume overload is considered a significant risk, hospitalization should be considered.

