Anti-hyperuricemic agents: Anti-hyperuricemic agents should be administered 2 to 3 days prior to starting treatment with venetoclax and may be continued through the titration phase.

Laboratory Assessments:

PRE-DOSE LABS

Prior to the initial dose of venetoclax, for all subjects:

- During the Screening Period: For all subjects, the chemistry/hematology panel (see [Table 4](#) Clinical Laboratory Tests) is required.
 - Pre-existing abnormalities should be corrected
- Within 72 hours of Week 1 Day 1: If the screening labs were more than 72h before the planned first dose, the chemistry/hematology panel should be repeated. These results should be reviewed before dosing.
 - Labs should be assessed and pre-existing abnormalities should be corrected
- On the day of Week 1 Day 1: Before dosing, the chemistry/hematology panel should be drawn. The results of the labs drawn on Week 1 Day 1 need to be reviewed prior to dosing **IF** an additional lab within 72 hours of the initial dose at Week 1 Day 1 was not drawn **AND** reviewed.

Prior to each subsequent dose increase, for all subjects:

- Within 72 hours of each subsequent dose increase: The chemistry/hematology panel should be repeated. The results should be reviewed prior to dose increasing.
- Prior to dosing, on the day of each subsequent dose increase: Before dosing, the chemistry/hematology panel should be drawn. The results of the labs drawn on Day 1 of each dose increase need to be reviewed prior to dosing **IF** an additional lab draw within 72 hours of the dose increase were not drawn **AND** reviewed.

POST-DOSE LABS:

For all subjects, the chemistry/hematology panel (refer to [Table 4](#) Clinical Laboratory Tests) should be monitored at 6 to 8 hours and at 24 hours after the first dose of venetoclax (20 mg) and after the first dose increase (50 mg). Electrolyte abnormalities should be corrected promptly. The next venetoclax doses (Day 2 20 mg venetoclax dose and Day 2 50 mg venetoclax dose) should not be administered until the 24 hour lab results have been evaluated. Electrolyte abnormalities should be corrected promptly. For subjects who continue to be at risk of TLS, the same lab monitoring schedule (i.e., 6 to 8 hour and 24-hr post dose) should be followed at the subsequent dose increases.

This monitoring is also recommended during the re-initiation of the therapy after a dose interruption.

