 - i. For all subjects, on the day of Week 1 Day 1, before dosing, the chemistry/hematology panel should be collected. The results of the labs drawn on Week 1 Day 1 need to be reviewed prior to dosing **IF** an additional lab within 72 hours of the initial dose at Week 1 Day 1 was not drawn **AND** reviewed.
 - j. For all subjects, the chemistry/hematology panel should be monitored at 6 to 8 hours and at 24 hours after the first dose of venetoclax (20 mg) and after the first dose increase (50 mg). The next venetoclax doses should not be administered until the 24 hour lab results have been evaluated. Electrolyte abnormalities should be corrected promptly.
Note: There is a ± 2 hour window around the 24 hour lab draw.
 - k. For all subjects, within 72 hours of each subsequent dose increase, the chemistry/hematology panel should be repeated. The results should be reviewed prior to dose increasing.
 - l. Prior to dosing, on the day of each subsequent dose increase, the chemistry/hematology panel is required. The results of the labs drawn on Day 1 of each dose increase need to be reviewed prior to dosing **IF** additional labs within 72 hours of the dose increase were not drawn **AND** reviewed.
 - m. For subjects who continue to be at risk of TLS, the same lab monitoring schedule of 6 to 8 hour and 24-hr post dose should be followed at the subsequent dose increases.
Note: There is a ± 2 hour window around the 24 hour lab draw.
-

- n. All measurable disease must be documented at Screening by laboratory testing, physical examination and CT scans (or MRI if CT is medically contraindicated); bone marrow examinations are not required at screening but results will be recorded if available. All baseline evaluations should be performed as closely as possible to the beginning of treatment. For all subsequent disease assessments, disease response will be assessed by the investigator based on the analysis of clinical laboratory tests (hematology) and a complete physical examination at Week 24, Week 36 and Week 48.

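### Subjects still at TLS risk have a 24-hour draw after the 100, 200 and 400 mg increases, but only the Day 2 20 mg and 50 mg doses must wait for the result

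*Protocol*

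**What the plan says.** Titration runs in weekly steps of 20, 50, 100, 200 and 400 mg (Protocol Sections 5.1 and 5.5.4). Section 5.3.1.1, under post-dose labs, sets a chemistry/hematology panel at 6 to 8 hours and at 24 hours for all subjects after the first 20 mg dose and after the increase to 50 mg. It attaches a hold to those two steps: "The next venetoclax doses (the Day 2 20 mg venetoclax dose and the Day 2 50 mg venetoclax dose) should not be administered until" the 24-hour results have been evaluated.

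For subjects who remain at risk of TLS, the text adds that "the same lab monitoring schedule (i.e., 6 to 8 hour and 24-hr post dose) should be followed at the subsequent dose increases". The words after the i.e. define the schedule as draw times.

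Section 6.1.8.1 repeats the hold for the same two named doses: "Day 2 20 mg venetoclax dose and Day 2 50 mg venetoclax dose) should not be administered until the 24 hour lab results" are evaluated. In Appendix D, footnote j, attached to Day 2 of Weeks 1 and 2, says "The next venetoclax doses should not be administered until the 24 hour lab results have been evaluated". Footnote m, attached to Day 2 of Weeks 3, 4 and 5, says only that "the same lab monitoring schedule of 6 to 8 hour and 24-hr post dose should be followed at the subsequent dose increases".

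The subjects concerned come back for this purpose. Section 5.1 states: "Additional study visits on Day 2 of each week should be performed for subjects who continue to be at risk for TLS", on the investigator's assessment.

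**The concern.** A 24-hour sample after a dose increase protects the subject most if it is read before the next dose is taken. At 100, 200 and 400 mg the plan collects the sample but does not say that it must be read first. These are the three highest dose levels, and the subjects affected are those already judged to be still at risk.

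The protocol does not treat the risk as over after 50 mg. Section 6.1.8.1 says that electrolyte changes needing prompt management can occur as early as 6 to 8 "hours following the first dose of venetoclax and at each dose increase".

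What is at stake is patient safety during titration. The point does not touch sample size, power or any efficacy analysis, and the SAP does not deal with it.

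**Working it through.** The check is mainly a comparison of text, followed by simple timing arithmetic. The plan states no figure of its own on this point.

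**1. Every place where the post-dose lab rule appears**

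| Place | 20 and 50 mg (all subjects) | 100, 200 and 400 mg (subjects still at risk) |
|---|---|---|
| Section 5.3.1.1 | Draws at 6–8 h and 24 h; Day 2 dose waits | Draws at 6–8 h and 24 h; no wait stated |
| Section 6.1.8.1 | Draws at 6–8 h and 24 h; Day 2 dose waits | Draws at 6–8 h and 24 h; no wait stated |
| Appendix D | Footnote j (W1 D2, W2 D2): draws and wait | Footnote m (W3 D2, W4 D2, W5 D2): draws only |

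All three places agree. For at-risk subjects the 24-hour draw applies at 5 levels and the wait at 2 of them, which leaves 5 − 2 = 3 levels with a draw and no wait.

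**2. Whether a general hold rule closes the gap**

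- Section 6.1.8.2 and Table 7 withhold the next day's dose at any level, once chemistry changes suggestive of TLS have been seen.
- Appendix H, Section 1 covers any dose escalation and stops dosing, if a laboratory criterion is met.
- Appendix H, Section 2 covers values at more than 24 hours and acts on a change that is already known.

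Each rule starts from a result in hand. None tells the site to have the 24-hour result before giving the Day 2 dose. They do catch an abnormality seen at 6–8 hours, and they stop later doses once the 24-hour result is read.

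**3. Timing on Day 2**

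Inputs: a window of ±2 hours around the 24-hour draw (Appendix D, footnotes j and m); once-daily dosing at about the same time each morning, so the Day 2 dose is due at about 24 h; and the late-dose rule in Section 5.5.1, "If the subject misses a dose of venetoclax within 8 hours of the time it is taken, the subject should take the missed dose" the same day.

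- Draw: 24 − 2 = 22 h to 24 + 2 = 26 h after the Day 1 dose.
- A compliant draw can follow the Day 2 dose by up to 26 − 24 = 2 h when nothing holds that dose. Footnote j has the same window, but its hold prevents this.
- Latest permitted Day 2 dose: 24 + 8 = 32 h.
- Time available for a result if the dose is held: 32 − 26 = 6 h to 32 − 22 = 10 h.

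**4. Exposure**

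The unread result affects at most 1 dose per level, because later doses fall under the general rules once the result is read. Over three levels this is 3 × 1 = 3 doses per still-at-risk subject at most, in an uninterrupted titration. The documents do not say how many subjects remain at risk after 50 mg. The possible range is 0 to all of the approximately 250 enrolled.

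**The case against.** The strongest reply is that the remaining gap is one narrow case: the 6–8 hour sample is clean, the change first shows at 24 hours, and the site doses before reading the result. Several safeguards surround that case. The general hold rules apply at every level. Section 5.3.1.1 uses local laboratories so that results can guide immediate management, and it allows extra monitoring. Section 5.5.4 permits risk-based delay or reduction, and Section 6.1.8.1 has hospitalization considered at later increases. The subject is on site on Day 2 and may be dosed there.

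The lighter rule may also be deliberate, because the protocol says that risk can fall as tumor burden falls. The Introduction reports no clinical or laboratory TLS in an analysis made after titration and prophylaxis were introduced. Finally, this protocol version is dated 12 October 2020 and extends late access, so initial titration was probably complete by then. That is an inference.

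Much of this stands as a limit on size. The later draws are also worded as something that should be done, so calling them required is slightly strong; the existing hold uses the same verb.

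Two parts do not stand. The safeguards act on a result already seen or set no deadline before the dose, so they do not replace the review. Falling risk is a reason to drop the draw for subjects no longer at risk, but not to leave the result unread before dosing those judged still at risk. As for the reported TLS experience, the documents do not describe the hold rules used then, so it cannot show that the present wording is enough.

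**Conclusion.** The concern holds. For subjects still at risk of TLS, 3 of the 5 titration levels have a 24-hour draw with no instruction to read it before the Day 2 dose, and a fully compliant site could give that dose unread. It does not contradict the dose-modification rules, which still stop dosing once an abnormality is known.

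The size is limited: at most 3 doses per affected subject. This assumes an uninterrupted titration and that each 24-hour result is read before the following day's dose. Re-titration after an interruption could add steps, since the same monitoring is recommended then. The number of affected subjects cannot be derived from the documents, and nothing here estimates how often harm would follow. Many sites may wait anyway. The change is worth making because it is cheap and makes that practice uniform.

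**What to change.** In Section 5.3.1.1, Section 6.1.8.1 and Appendix D footnote m, directly after the sentence on later dose increases, add one sentence saying that for these subjects the next dose is to be held until the 24-hour results have been evaluated. Using the wording of the existing hold would keep the rule identical at every increase where the draw is done.

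This needs no new visits or draws. The usual cost is a same-day delay of one dose per affected step, within the 6 to 10 hours that the late-dose allowance leaves. If a local result took longer, that dose would be skipped under Section 5.5.1, as can already happen at 20 mg and 50 mg.

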5.3.1.2 Collection and Handling of Biomarker Research Samples

Biospecimens may be utilized to evaluate known and/or novel disease-related or drug-related biomarkers. The biomarker rationale will be discussed in the Biomarker Research Variables Section (Section 5.3.6).

Biomarker Samples

Minimal Residual Disease (MRD) Assessment

Peripheral blood for MRD will be collected from all subjects as outlined in [Appendix D](#) and [Appendix E](#).

When confirming a CR or CRi status per the 2008 Modified IWCLL NCI-WG criteria with a bone marrow biopsy, whenever possible, a bone marrow aspirate should be

collected for MRD assessment. The bone marrow aspirate should be split and a sample sent to the Central Laboratory.

All biomarker samples should be labeled and shipped as outlined in the study-specific laboratory manual.

AbbVie (or people or companies working with AbbVie) will store the samples in a secure storage space with adequate measures to protect confidentiality. The samples may be retained while research on venetoclax, or drugs of this class, or this disease and related conditions continues, but for no longer than 20 years after study completion, or per local requirement.

5.3.2 Drug Concentration Measurements

5.3.2.1 Collection of Samples for Analysis

Blood samples for venetoclax and possible metabolite(s) will be collected by venipuncture per [Appendix D](#) and [Appendix E](#). The date and time (to the nearest minute) of the last dose and second to last dose of venetoclax will be recorded on the eCRF. The date and time (to the nearest minute) of each blood sample collection will be recorded on the sample requisition form.

Blood samples (3 mL) for venetoclax assay will be collected at the following time:

- Week 24 Day 1: 0 hour (pre-dose)

A total of 1 blood sample is planned to be collected per subject for venetoclax PK analysis. Refer to the study specific laboratory manual for detailed instructions on sample collection, processing, and shipment.

5.3.2.2 Measurement Methods

Plasma concentrations of venetoclax will be determined by the Drug Analysis Department at AbbVie using validated methods. Plasma concentrations of other possible metabolites from venetoclax may be determined with validated or non-validated methods.

5.3.3 Efficacy Variables

The primary objective of this study is to evaluate the efficacy of venetoclax monotherapy in subjects with relapsed or refractory chronic lymphocytic leukemia (CLL). The primary efficacy endpoint will be measured by complete remission rate (CR + CRi) of the subjects who have not been previously treated with B-cell receptor inhibitor (BCRi) therapy, as assessed by the investigator.

The secondary objectives are to evaluate other efficacy parameters including the overall response rate (ORR), duration of overall response (DoR), time to progression, (TTP), progression-free survival (PFS), overall survival (OS), and the CR rate in BCRi treated subjects.

Additional secondary objectives will be evaluated. Health Economic and Patient-Reported Outcome Measures will include the EQ-5D-5L, the FACT-Leu and the FACIT-F. Minimal residual disease (MRD) and the rate of MRD negativity in the peripheral blood are assessed as exploratory objectives in the peripheral blood and bone marrow (BM) by flow cytometry, PCR and/or sequencing.

Analyses of these endpoints are described in Section [8.0](#).

5.3.3.1 Primary Variables

For disease assessments, response will be assessed by the investigator based on analysis of clinical laboratory tests (hematology laboratory values), disease assessment physical examination, CT scan including neck, chest, abdomen, and pelvis (or MRI if CT with contrast is medically contraindicated); bone marrow aspirate are not required but results will be recorded if available. Subjects will be evaluated against the 2008 Modified

IWCLL NCI-WG Criteria for Tumor Response⁴⁶ with CT imaging (or MRI). A BM sample assessment is required to confirm CR.

At screening (baseline), all measurable disease must be documented by laboratory testing (hematologic status), physical examination, and CT scan. All baseline evaluations should be performed as closely as possible to the beginning of treatment and not more than 4 weeks before the beginning of the treatment with the exception of the CT scan (or MRI) which will be accepted if previously performed within 35 days prior to study drug initiation. During the study, subjects will have a disease assessment at Week 24, Week 36 and Week 48. To confirm the response, a CT scan will be performed at Week 48 on all subjects. For subjects with CR as response at Week 48, a BM sample is required to confirm the response.

Methods of Measurement

Disease response and progression will be assessed by analysis of peripheral blood, clinical examination, radiographic scans and bone marrow aspirate and biopsy.

The same method of assessment and the same technique should be used to characterize each identified and reported lesion at baseline and during follow-up.

Details on the analysis of peripheral blood required to assess response are provided in Section [5.3.1.2](#).

A full disease assessment physical examination should be performed to assess the extent of disease involvement. Physical examinations should include the evaluation of the presence and degree of enlarged lymph nodes in two dimension (cervical, supraclavicular, axillary, inguinal and femoral nodes), hepatomegaly, and splenomegaly. These should be noted on all examinations irrespective of being present or absent. All measurements should be taken and recorded in metric notation using a ruler or calipers. Clinical lesions will only be considered measurable when they are superficial (e.g., palpable lymph nodes). The diameter, in two planes, of the largest palpable nodes in each of the

following sites should be measured: cervical, supraclavicular, axillary, inguinal, and femoral. The presence of hepatomegaly and splenomegaly should be performed.

The 12 largest bi-dimensional lesions should be recorded in the eCRF.

- Target Lesions: A maximum of 12 target lesions may be selected (up to 6 nodal and 6 extra nodal). Target nodal lesions must be abnormal (> 1.5 cm in LDi [Longest Diameter] at baseline), clearly measurable and suitable for consistent, reproducible measurement in at least two perpendicular dimensions. Target extra nodal lesions must be > 1 cm in two perpendicular diameters at baseline.
- Non-Target Lesions: Sites will be classified as non-target lesions where disease is present but not selected for target lesions. A maximum of 10 non-target lesions can be selected. Non-target nodal lesions must be abnormal (> 1.5 cm in LDi at baseline). Non-target extra nodal lesions must be > 1 cm in two perpendicular diameters. Nodal and extra nodal lesions that were not selected as target lesions at baseline can be followed as non-target lesions.

Computed tomography (CT) is the preferred method to measure lesions selected for response assessment. CT scans (with contrast) should include neck, chest, abdomen, and pelvis scans. CT scans for response assessment may be limited to areas of prior involvement only, if required by local regulatory authorities. A contrast-enhanced MRI of the neck, chest, abdomen and pelvis with a non-contrast CT scan of the chest may be used if CT with contrast is medically contraindicated (e.g., severe contrast allergy). If MRIs are used instead of CT scans, MRIs should be used consistently throughout the study. Conventional CT and MRI should be performed with cuts of 5 mm or less in slice thickness contiguously. Spiral CT should be performed by use of 5 mm contiguous reconstruction algorithm; this specification applies to the regions of the neck, chest, abdomen and pelvis at baseline and follow-ups. The 12 largest bi-dimensional lesions should be recorded in the eCRF (6 nodal and 6 extra nodal).

For accurate overall response evaluation, ultrasound (US) should not be used to measure tumor lesions.

Details on bone marrow biopsy and aspirate are provided in Section 5.3.1.1. Study Procedures.

Tumor Response Criteria

Complete Remission (CR)

CR requires all of the following criteria:

- Peripheral blood lymphocytes (evaluated by blood and differential count) below $4 \times 10^9/L$ (4000/ μL)
- Absence of lymphadenopathy (nodes > 15 mm in longest diameter or any extra nodal disease) by physical examination and CT scan
- No hepatomegaly or splenomegaly by physical examination (as determined by measurement below the relevant costal margin)
- Absence of disease or constitutional symptoms (B symptoms: unexplained fevers > 38°C or 100.4°F, drenching night sweats, > 10% body mass weight loss in the preceding 6 months)
- Blood counts above the following laboratory values:
 - Neutrophils > $1.5 \times 10^9/L$ [1500/ μL] (without the need for exogenous growth factors)
 - Platelets > $100 \times 10^9/L$ [100,000/ μL] (without the need for platelet transfusion or exogenous growth factors)
 - Hemoglobin > 110 g/L [11 g/dL] (without the need for blood transfusions or exogenous erythropoietin)
- Bone marrow at least normocellular for age, < 30% of nucleated cells being lymphocytes. Lymphoid nodules should be absent. Bone marrow aspirate and biopsy should be performed after CR/CRi has been achieved. If the bone marrow is hypocellular, a repeat determination should be made in 4 weeks or when peripheral blood counts have recovered. A marrow biopsy should be compared to a pre-treatment marrow if available. Subjects who are otherwise

in a complete remission, but bone marrow nodules can be identified histologically should be considered to be nodular PR (nPR). Immunohistochemistry (IHC) should be performed to define whether these nodules are composed of primarily T cells or lymphocytes other than CLL cells, or CLL cells.

Complete Remission with Incomplete Marrow Recovery (CRi)

Subjects who fulfill the criteria for CR (including bone marrow) but who have persistent cytopenia (anemia or thrombocytopenia or neutropenia) apparently unrelated to CLL but related to drug toxicity will be considered CRi. The marrow evaluation described above should be performed with scrutiny and not show any clonal infiltrate.

Partial Remission (PR)

To be considered a PR at least 2 of the following must be met:

- $\geq 50\%$ decrease in peripheral blood lymphocyte count from the pretreatment baseline value.
- $\geq 50\%$ reduction in lymphadenopathy.
- $\geq 50\%$ reduction in the size of the liver and/or spleen (if abnormal prior to therapy).

In addition at least **one** of the following criteria must be met:

- Neutrophils $> 1,500/\mu\text{L}$ or $\geq 50\%$ improvement over baseline.
- Platelets $> 100,000/\mu\text{L}$ or $\geq 50\%$ improvement over baseline.
- Hemoglobin $> 11.0 \text{ g/dL}$ or $\geq 50\%$ improvement over baseline without transfusions or exogenous growth factors.

Table 5. 2008 Modified IWCLL NCI-WG Criteria for Tumor Response

Parameter	Complete Remission (CR) All Criteria Must be Met^a	Partial Remission (PR) at Least 2 Criteria from Group A AND at Least 1 Criterion from Group B Must be Met	Progressive Disease (PD) at Least 1 Criterion from Group A OR 1 Criterion from Group B Must be Met^b	Stable Disease (SD) All Criteria Must be Met
Group A				
Lymphadenopathy	None > 1.5 cm	Decrease \geq 50% ^c	Increase \geq 50% ^d or any new LN > 1.5 cm	Change of -49% to +49% ^e
Blood Lymphocytes	< 4000/ μ L	Decrease \geq 50% from baseline	Increase \geq 50% over baseline (\geq 5000/ μ L)	Change of -49% to +49%
Hepatomegaly ^f	None	Decrease \geq 50%	Increase \geq 50% ^g	Change of -49% to +49%
Splenomegaly ^f	None	Decrease \geq 50%	Increase \geq 50% ^g	Change of -49% to +49%
Marrow	Normocellular, < 30% lymphocytes, no B lymphoid nodules; hypocellular marrow defines CRi	N/A	N/A	N/A
Group B				
Platelet Count	> 100,000/ μ L ^h	> 100,000/ μ L or increase \geq 50% over baseline ^h	Decrease of \geq 50% from baseline secondary to CLL	Change of -49% to +49%
Hemoglobin	> 11.0 g/dL ^h	> 11.0 g/dL or increase \geq 50% over baseline ^h	Decrease of > 2 g/dL from baseline secondary to CLL	Increase to \leq 11.0 g/dL over baseline, or decrease < 2 g/dL
Neutrophils	> 1500/ μ L ^h	> 1500/ μ L or increase \geq 50% over baseline ^h	Decrease \geq 50% from baseline secondary to CLL	N/A
New Lesions	None	None	Appearance of new palpable lymph nodes (> 1.5 cm in longest diameter) or any new extra nodal lesion (regardless of size) or transformation to a more aggressive histology, e.g., Richter Syndrome ^d	None

Table 5. 2008 Modified IWCLL NCI-WG Criteria for Tumor Response (Continued)

Parameter	Complete Remission (CR) All Criteria Must be Met ^a	Partial Remission (PR) at Least 2 Criteria from Group A AND at Least 1 Criterion from Group B Must be Met	Progressive Disease (PD) at Least 1 Criterion from Group A OR 1 Criterion from Group B Must be Met ^b	Stable Disease (SD) All Criteria Must be Met
Other Considerations				
Non-Target Lesions	Nodes must be normal size as visually estimated; extra nodal and other assessable disease should be absent	No change/decreased	Unequivocal progression	No change or decrease or non-substantial increase
Target Extra Nodal Disease	Absence of any extra nodal disease by physical examination (palpable, visualized extra nodal) and CT scan	≥ 50% decrease in SPD	≥ 50% increase in the longest diameter of any extra nodal lesion	Not CR, CRi, PR, or PD

CLL = chronic lymphocytic leukemia; LN = lymph nodes; N/A = Not applicable; SPD = sum of the products of diameters; CRi = complete remission with incomplete marrow recovery

- a. CR also requires the lack of disease-related constitutional symptoms.
- b. Transformation to a more aggressive histology (e.g., Richter Syndrome) would also qualify as a PD.
- c. Sum of the products of multiple LNs (as evaluated by CT scans). Note in eCRF if by physical examination only.
- d. Increase in SPD of multiple nodes, or in greatest diameter of any previous site, or appearance of any new lymphadenopathy or organomegaly. Degree of change in LN or lymphocyte counts should be measured from nadir (lowest post-treatment) values.
- e. Sum products of up to 6 LNs or LN masses (target lesions), with no increase in an LN or new enlarged LN. Increase of < 25% in small LNs (< 2 cm) not significant. Decreases should be measured compared to baseline (pre-treatment) values.
- f. If enlarged before therapy.
- g. An increase in the previously noted enlargement of the liver or spleen by 50% or more or the de novo appearance of hepatomegaly or splenomegaly.
- h. Without the need for exogenous growth factors or transfusions.

